**Questionnaire 1 – proxy – after 3 months**

Enquêtevragen als proxy (familielid of partner) toestemming heeft gegeven voor deelname aan het onderzoek.

[voor start vragenlijst: informatie deferred consent en redenen voor dit onderzoek]

Algemeen

- Geslacht
  - Man
  - Vrouw
- Leeftijd (vrije tekst)

Wat is uw hoogst genoten opleiding? (keuze)

- geen
- basisschool
- lager beroepsonderwijs (LBO, VMBO)
- middelbaar algemeen voorbereidend onderwijs (MAVO)
- middelbaar beroepsonderwijs (MBO)
- hoger algemeen voorbereidend, wetenschappelijk onderwijs (HAVO, VWO)
- hoger beroepsonderwijs (HBO)
- kandidaats/propedeuse wetenschappelijk onderwijs (WO)
- (post) wetenschappelijk onderwijs
- weet niet / wil ik niet zeggen

Vragen over verloop toestemmingsprocedure en methode van het onderzoek

1. Vindt u zelf dat u voldoende weet over het onderzoek?

I. Ik vind dat ik voldoende weet over het **doel** van het onderzoek

- Ja
- Nee

II. Ik vind dat ik voldoende weet over de **opzet** van het onderzoek

- Ja
- Nee

2. Heeft u de informatiebrief gelezen?

- Ja
- Nee

3. Heeft u de informatiebrief begrepen?

- Ja
- Nee

4. Welke behandeling werd in dit onderzoek getest? (vrije tekst)

5. Hoe werd besloten welke behandeling u kreeg? (vrije tekst)

6. Welke behandeling heeft u of uw naaste gekregen? (vrije tekst)

7. Waren er risico's en nadelen verbonden aan meedoen aan het onderzoek? (ja/nee + vrije tekst)

8. Waren er voordelen verbonden aan meedoen aan het onderzoek? (ja/nee + vrije tekst)

9. Was deelname aan het onderzoek vrijwillig of verplicht?

- Vrijwillig
- Verplicht

10. Was het mogelijk uw toestemming voor deelname aan het onderzoek in te trekken?

- Ja
- Nee

11. Wie had toegang tot uw persoonlijke gegevens en ziektegeschiedenis? (vrije tekst)

Vragen over uw waardering van de toestemmingsprocedure

12. Voelde u zich destijds in staat om te beslissen over deelname aan dit onderzoek?

- Ja (ga naar vraag 16)

- Nee (ga hieronder verder)

13. Wie had u liever deze beslissing willen laten maken?

- Mijn behandelend arts
- Een familielid, namelijk: .....
- Toestemming voor dit onderzoek vind ik niet nodig

14. Waarom voelde u zich niet in staat om te beslissen over deelname aan dit onderzoek?  
(meerdere antwoorden mogelijk)

- I. Ik vond het te veel informatie
- II. Ik begreep de uitleg niet goed
- III. Ik voelde mij gestresst
- IV. Deze vraag kwam te snel na de beroerte
- V. Ik heb te weinig bedenktijd gehad
- VI. Anders, namelijk: .....

15. Had u genoeg tijd om een beslissing te maken?

- Ja
- Nee

16. Had u liever gewild dat de vraag voor deelname aan het onderzoek op een ander moment was gekomen?

- Ja (ga naar de volgende vraag)
- Nee (ga naar vraag 19)

17. Zo **ja**, op welk moment had u liever gewild dat deze vraag aan u was gesteld? (één keuze)

- Eerder: nog vóór alle studiehandelingen, inclusief de behandeling
- Eerder na de studiehandelingen: binnen 12 uur in plaats van binnen 24 uur
- Later: binnen 72 uur in plaats van binnen 24 uur

[figure not shown]
18. U hebt als familielid de beslissing voor uw naaste gemaakt. Welke beslissing zou uw naaste zelf hebben gemaakt?

- Meedoen met het onderzoek
- Niet meedoen met het onderzoek

19. Als de toestemmingsprocedure op een later tijdstip had plaatsgevonden (bijvoorbeeld binnen 72 uur in plaats van binnen 24 uur), zou u ermee akkoord gaan als er dan ook meer studiehandelingen (zoals bloedprikken of een CT-scan van het hoofd) zouden zijn uitgevoerd?

- Ja
- Nee

20. Hoe ervaart u de uitgestelde toestemmingsprocedure? (onderstaande Likert schaal + vrije tekst)

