### ***Tertiary objectives***

To collect and analyse data regarding the deferred consent procedure and its association with patient recall and satisfaction at three months from randomisation.

To study the efficiency of national IAT implementation, given the availability of IAT hospitals and capacity, and travel times of ambulance services. To this end, we aim to collect data (time delays and diagnostics) from each step in the acute stroke pathway as input parameters for a simulation model. This way we can study the regional set-up of the IAT organisational model.

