If the subject is considered mentally competent to provide consent, the subject will be informed and asked for consent. However, if the subject lacks decision-making capacity, the investigator will search for a legal representative available. Every 24 hours, the investigator will assess whether the subject or the legal representative is capable of making a decision about participation in this trial in the current situation. If not, every 24 hours later will be evaluated if informed consent can be obtained. If there is no legal representative available, study procedures will be continued until a proxy is present.

The subject and/or his/her legal representative will be given sufficient time to read the ICF and the opportunity to ask questions. However, this time period is limited to the duration of the hospital admission. After this explanation, consent should be appropriately recorded by means of the subject's or the legal representative's personally dated signature and authorised study staff's personally dated signature. After obtaining the consent, a copy of the ICF must be given to the subject.

Copies or a second original of the signed ICF will be given to the subject and the original will be maintained with the subject's records. If new safety information results in significant changes in the risk/benefit assessment, the ICF should be reviewed and updated if necessary. All subjects for whom this is relevant should be informed of the new information and give their consent to continue the study.

If a patient who has been enrolled into the study refuses to participate and sign the ICF, or if his/her legal representative refuses this in case of the patient's incapacity, participation into the study will be terminated immediately. Data from non-consenting subjects will only be used when there is no written objection from the subject or representative. In an effort to describe the non-consenting population we will ask the subject or his/her representative to allow the use of routinely collected data in a coded manner. The refusal and the reason, if available, will be recorded in the patient's clinical chart.

If a patient has died before deferred consent has been obtained, his/her representative will be informed about the study treatment the patient may have received, trial procedures and use of the collected data. A separate information letter will be sent to a representative of the patient.

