### Duration of data collection

We aim to collect data on deferred consent of 300 patients during the first year of enrolment in the CONTRAST trials. Data collection will start 3 months after the first inclusion in the study.

**Patient recruitment**Patients / proxies who provided consent for participation in the trial

During the 3 month telephone follow-up of the CONTRAST trial, the subject who provided consent will be asked to participate in this substudy. The purpose of the study will be explained and the study procedures will be described. Questionnaire 1 will be sent to their home address. The feeling of capability for giving consent, appreciation of the informed consent process and recall and comprehension will be explored in this questionnaire. For participation in this substudy, no additional written informed consent from individual subjects is needed.

Patients / proxies who withheld consent for participation in the trial

The patient or proxy who refused to give deferred consent for participation in the CONTRAST trial will be approached. The purpose of the study will be explained and the study procedures will be described. They will be asked to only fill out Questionnaire 2, which concerns the reasons for not giving consent. It will be emphasized that it is not mandatory to answer. No additional questionnaires or interviews will be carried out within this patient group.

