## 2. Deferred consent workflow and timeline

The study protocols of the CONTRAST trials state that deferred informed consent will be obtained within the first 24 hours after enrolment. In the MR ASAP trial, the nitroglycerin patch will be removed after 24 hours. However, when a patient refuses to provide consent, the patch will be removed directly. For the subsequent CONTRAST trials, the first follow-up CT scan will be performed 24 hours after randomisation (Figure 1).

We will document time intervals from symptom onset until consent has been obtained. The timeline will contain the following time measurements, if applicable.

1. MR ASAP: onset – randomisation/treatment – ER – inclusion in subsequent CONTRAST trial – IVT – IAT – start IC conversation – signature patient/proxy
2. MR CLEAN-NO IV: onset – inclusion in MR ASAP – ER – randomisation – IVT – IAT – start IC conversation – signature patient/proxy
3. MRCLEAN-MED: onset – inclusion in MR ASAP – ER – IVT – randomisation – IAT – start IC conversation – signature patient/proxy
4. MRCLEAN-LATE: onset – inclusion in MR ASAP – ER – IVT – randomisation – IAT – start IC conversation –signature patient/proxy

*ER: emergency room; IVT: intravenous thrombolysis; IAT: intra-arterial treatment; IC: informed consent*

On the ICF we will record date and time of:

- start of informed consent conversation; and
- signature of patient or proxy.

The remaining time measurements will be recorded in the electronic case report form (eCRF).

We will compare of the numbers and time intervals of patient vs. proxy consent in our study with data from the Multicenter Randomized CLinical trial of Endovascular treatment for Acute Ischemic stroke in the Netherlands (MR CLEAN).

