**Questionnaire 1 – patient – after 3 months**

Enquêtevragen als patiënt toestemming heeft gegeven voor deelname aan het onderzoek.  
[voor start vragenlijst: informatie deferred consent en redenen voor dit onderzoek]

Algemeen

Wat is uw hoogst genoten opleiding? (keuze)

- geen
  
- basisschool
  
- lager beroepsonderwijs (LBO, VMBO)
  
- middelbaar algemeen voorbereidend onderwijs (MAVO)
  
- middelbaar beroepsonderwijs (MBO)
  
- hoger algemeen voorbereidend, wetenschappelijk onderwijs (HAVO, VWO)
  
- hoger beroepsonderwijs (HBO)
  
- kandidaats/propedeuse wetenschappelijk onderwijs (WO)
  
- (post) wetenschappelijk onderwijs
  
- weet niet / wil ik niet zeggen

Vragen over uw kennis en begrip over de methode van het onderzoek

1. Vindt u zelf dat u voldoende weet over het onderzoek?

I. Ik vind dat ik voldoende weet over het **doel** van het onderzoek

- Ja
  
- Nee

II. Ik vind dat ik voldoende weet over de **opzet** van het onderzoek

- Ja
  
- Nee

2. Heeft u de informatiebrief gelezen?

- Ja
  
- Nee

3. Heeft u de informatiebrief begrepen?

- Ja
- Nee

4. Welke behandeling werd in dit onderzoek getest? (vrije tekst)

5. Hoe werd besloten welke behandeling u kreeg? (vrije tekst)

6. Welke behandeling heeft u of uw naaste gekregen? (vrije tekst)

7. Waren er risico's en nadelen verbonden aan meedoen aan het onderzoek? (ja/nee + vrije tekst)

8. Waren er voordelen verbonden aan meedoen aan het onderzoek? (ja/nee + vrije tekst)

9. Was deelname aan het onderzoek vrijwillig of verplicht?

- Vrijwillig
- Verplicht

10. Was het mogelijk uw toestemming voor deelname aan het onderzoek in te trekken?

- Ja
- Nee

11. Wie had toegang tot uw persoonlijke gegevens en ziektegeschiedenis? (vrije tekst)

Vragen over uw waardering over de toestemmingsprocedure

12. Voelde u zich destijds in staat om te beslissen over deelname aan dit onderzoek?

- Ja (ga naar vraag 16)
- Nee (ga hieronder verder)

13. Wie had u liever deze beslissing willen laten maken?

- Mijn behandelend arts
- Een familielid, namelijk: .....
- Toestemming voor dit onderzoek vind ik niet nodig

14. Waarom voelde u zich niet in staat om te beslissen over deelname aan dit onderzoek?  
(meerdere antwoorden mogelijk)

- I. Ik vond het te veel informatie
- II. Ik begreep de uitleg niet goed
- III. Ik voelde mij gestresst
- IV. Deze vraag kwam te snel na de beroerte
- V. Ik heb te weinig bedenktijd gehad
- VI. Anders, namelijk: .....

15. Had u genoeg tijd om een beslissing te maken?

- Ja
- Nee

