16. Had u liever gewild dat de vraag voor deelname aan het onderzoek op een ander moment was gekomen?

- Ja (ga naar de volgende vraag)
- Nee (ga naar vraag 19)

17. Zo **ja**, op welk moment had u liever gewild dat deze vraag aan u was gesteld? (één keuze)

- Eerder: nog vóór alle studiehandelingen, inclusief de behandeling
- Eerder na de studiehandelingen: binnen 12 uur in plaats van binnen 24 uur
- Later: binnen 72 uur in plaats van binnen 24 uur

18. Had u het goed vonden als een familielid voor u deze beslissing had gemaakt?

- Ja
- Nee

19. Welke beslissing zou uw familielid hebben gemaakt, als uw familielid voor u deze beslissing had gemaakt?

[figure not shown]
- Meedoen met het onderzoek

- Niet meedoen met het onderzoek

20. Als de toestemmingsprocedure op een later tijdstip had plaatsgevonden (bijvoorbeeld binnen 72 uur in plaats van binnen 24 uur), zou u ermee akkoord gaan als er dan ook meer studiehandelingen (zoals bloedprikken of een CT-scan van het hoofd) zouden zijn uitgevoerd?

- Ja
- Nee

21. Hoe ervaart u de uitgestelde toestemmingsprocedure? (onderstaande Likert schaal + vrije tekst)

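### Two skip rules in the three-month deferred-consent questionnaire (Questionnaire 1) withhold items 15 and 18 from respondents who should answer them, and its 24-hour premise conflicts with section 11.2

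*Protocol*

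**What the plan says.** The protocol's tertiary objectives (section 2) include "To collect and analyse data regarding the deferred consent procedure and its association with patient recall and satisfaction at three months from randomisation". Appendix 12 describes the substudy that serves this aim: "We aim to collect data on deferred consent of 300 patients during the first year of enrolment in the CONTRAST trials". People who gave consent receive Questionnaire 1 at three months, in a patient version of 21 items or a proxy version of 20.

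Both versions have the same two skip rules:

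- Item 12 asks whether the respondent felt able to decide. The Yes answer carries the instruction "Ja (ga naar vraag 16", which passes over items 13, 14 and 15.
- Item 16 asks whether another moment would have been preferred. The No answer carries the instruction "Nee (ga naar vraag 19", which passes over items 17 and 18.

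Item 18 differs between the versions. The patient version asks "18. Had u het goed vonden als een familielid voor u deze beslissing had gemaakt" (whether a relative's decision would have been acceptable). The proxy version asks "Welke beslissing zou uw naaste zelf hebben gemaakt" (what the patient would have decided).

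On timing, Appendix 12 (Deferred consent workflow and timeline) says that the CONTRAST protocols state that "deferred informed consent will be obtained within the first 24 hours after enrolment". Section 11.2 sets no such limit. It asks for consent as soon as is reasonable, reassesses capacity every 24 hours, and says of the time allowed for reading the form and asking questions that "this time period is limited to the duration of the hospital admission".

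**The concern.** A skip rule is sound when the skipped items make no sense for the person who skips them. Items 15 and 18 make sense for everyone. Whether there was enough time to decide does not depend on having felt unable to decide. What the other party would have wanted does not depend on a preference about timing.

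The items bear on the substudy's own rationale. The background in Appendix 12 argues that some patients do not want relatives to decide for them and that many proxies do not know the patient's wishes. Patient item 18 addresses the first point and proxy item 18 the second. Appendix 12 also says that the substudy's conclusions may change the actual consent procedure, so it matters who answered.

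The 24-hour premise is a separate matter. Item 17 allows one choice from three and has no open category. Two of the three options are framed as a change from consent within 24 hours. That reference does not fit someone who consented later, as section 11.2 permits.

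**Working it through.** The plan gives no power or precision figure for these items, so there is nothing to reproduce. The check is to trace the routes.

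**Routes.** Two filters with two answers each give four routes per version.

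| Item 12 | Item 16 | Items skipped | Patient items asked (of 21) | Proxy items asked (of 20) |
|---|---|---|---|---|
| No | Yes | none | 21 | 20 |
| No | No | 17, 18 | 19 | 18 |
| Yes | Yes | 13, 14, 15 | 18 | 17 |
| Yes | No | 13, 14, 15, 17, 18 | 16 | 15 |

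**Which skips are proper.** Item 13 (who should have decided instead), item 14 (why the respondent felt unable) and item 17 (which moment would have been better) follow from the filter answer. Of the five items that can be skipped, three are proper follow-ups and 5 − 3 = 2 are not: items 15 and 18.

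**The mirror items.**
- Patient item 19 asks what the relative would have decided. It lies on all four routes.
- Proxy item 18 asks what the patient would have decided. It lies only on the two routes with Yes at item 16.
- The proxy version has one item fewer, and the content of patient item 19 sits at proxy item 18. The target of 19 in the proxy form therefore looks carried over from the patient numbering.

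**Item 15.** It is reached only after No at item 12. Those respondents have just been offered too little time to reflect as a reason in item 14. Item 15 is thus close to redundant for those who see it and missing for everyone else.

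**Items on every route.** Items 1 to 12 (knowledge, recall, comprehension, felt capability), item 16 (timing preference) and the closing rating of the procedure (patient item 21, proxy item 20) have no filter.

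**Precision, as illustration only.** The share answering Yes at item 16 is not in the documents, so a range is assumed. The 95% half-width for a proportion of 0.5 is 1.96 × √(0.25/n). The base of 300 covers patients and proxies together, so each n below is an upper bound for either version.

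| Assumed Yes at item 16 | n answering item 18 | Half-width (percentage points) |
|---|---|---|
| 10% | 300 × 0.10 = 30 | 17.9 |
| 25% | 300 × 0.25 = 75 | 11.3 |
| 50% | 300 × 0.50 = 150 | 8.0 |
| 75% | 300 × 0.75 = 225 | 6.5 |
| everyone asked | 300 | 5.7 |

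The lost precision is secondary. The main defect is that the answers come from a group selected on an unrelated question.

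**The case against.** The strongest reply is that little depends on these two items. The tertiary objective concerns recall and satisfaction, and the items that measure them reach every Questionnaire 1 respondent. The specific objectives in Appendix 12 name neither agreement between proxy and patient nor adequacy of decision time. On the patient side, the relative's likely decision (item 19) is asked of all. The substudy is observational and descriptive. All of this stands, and it limits the point to two items per version.

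A reader might go further and infer that the tertiary objective as a whole is estimated in a dissatisfied minority. The documents do not support that:

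- No response shares are given, so nothing shows that most respondents are routed past these items.
- The figure of 300 is a target for patients with deferred-consent data across the CONTRAST trials, not a count of respondents to one form. Patient item 18 and proxy item 18 are also different questions that cannot be pooled.
- Wanting another moment may mean earlier or later, and feeling unable to decide is not the same as being dissatisfied. The direction of any bias is not shown.
- The 24-hour answer options route nobody. In patient item 20 and proxy item 19 the 24 and 72 hours are given only as an example, and the first option of item 17 (before any study procedure) keeps its meaning whenever consent was asked.
- Questionnaire 2 has no skip rules.

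The reply does not remove the routing fault. The jump targets are explicit in both versions, and no reason is given for withholding items 15 and 18.

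**Conclusion.** The point holds in a narrow form. In each version of Questionnaire 1, two items that everyone could answer are filtered on an unrelated answer. Item 15 will describe only people who felt unable to decide. Item 18 will describe only people who wanted another moment, and proxy item 18 cannot be set against patient item 19. How many respondents this affects is unknown, and the half-widths above rest on assumed shares and a pooled base.

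Separately, the 24-hour statement in Appendix 12 and section 11.2 do not agree, and item 17 is built on the former. The Appendix 10 flowchart is not reproduced in the text available, so it could not be compared.

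The matter is minor. It is confined to a descriptive substudy and does not touch the primary or safety analyses, but it is cheap to correct and decides which data are collected.

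**What to change.** - In both versions, send No at item 16 to item 18, and Yes at item 12 to item 15.
- Reconcile the 24-hour statement in Appendix 12 with the consent window in section 11.2, then align the options of item 17 with the reconciled text. One way is to word them as earlier or later than the respondent's own consent time, which Appendix 12 already records on the consent form.
- If forms have already gone out under the present routing, report items 15 and 18 from those forms with the filtered denominators stated.

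The cost is an amendment to the forms and at most two more items per respondent. On the shortest route the patient version goes from 16 to 16 + 2 = 18 items and the proxy version from 15 to 15 + 2 = 17. This should fit within the maximum of 30 minutes that Appendix 12 estimates for Questionnaire 1.

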**Questionnaire 2 – patient**

[voor start vragenlijst: informatie deferred consent en redenen voor dit onderzoek]

Enquêtevragen als patiënt om uitgestelde toestemming is gevraagd voor deelname aan de CONTRAST trial en geen toestemming heeft gegeven.

Wat was de reden dat u geen toestemming heeft gegeven? (meerdere opties mogelijk)

- Dit wil ik niet zeggen
- Ik wil niet dat er gegevens verzameld worden van mij
- Ik vond het te veel informatie
- Ik begreep de uitleg niet goed
- Ik voelde mij gestresst
- Deze vraag komt te snel na de beroerte
- Ik heb te weinig bedenktijd gehad
- Ik vind dat iemand anders, namelijk de behandelend arts deze beslissing voor mij moet maken
- Ik vind dat iemand anders, namelijk mijn partner en/of ander familielid deze beslissing voor mij moet maken
- Anders, namelijk: .....

Wat is uw hoogst genoten opleiding? (keuze)

- geen
- basisschool
- lager beroepsonderwijs (LBO, VMBO)
- middelbaar algemeen voorbereidend onderwijs (MAVO)
- middelbaar beroepsonderwijs (MBO)
- hoger algemeen voorbereidend, wetenschappelijk onderwijs (HAVO, VWO)
- hoger beroepsonderwijs (HBO)
- kandidaats/propedeuse wetenschappelijk onderwijs (WO)
- (post) wetenschappelijk onderwijs

weet niet / wil ik niet zeggen

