## Benefits and drawbacks of deferred consent

- Effect on treatment delays.

The use of the deferred consent procedure might reduce time to study (drug) treatment,

with potential beneficial effects, and reduce delay to standard stroke treatments since the CONTRAST trials will study adaptations of endovascular treatment. No disadvantages of deferred consent on treatment delays are expected.

- Influence on decision-making competence.

Decision-making competence is based on factual understanding, evidencing a choice (consent or refusal), and reasoning and appreciation of the situation. In the acute phase of an emergency situation, patients and relatives are in emotional distress and can be considered temporarily incompetent in these three points. Hence, patients and their relatives can be regarded temporarily incompetent for valid proxy consent in an emergency situation. Deferment of the conversation might lead to a more ethically valid informed consent and a better informed decision.

Still, there is no consistency in the duration of the acute phase of the emergency situation. The moment patients and proxies regain decision-making competence is not defined. Also, patients and proxies might not regard themselves competent of making a decision in the day(s) after the emergency situation.

In addition, some patients and proxies will feel capable of making a decision and could object to the deferred consent procedure itself because they not understand the reasons for the postponement of asking consent. This could interfere with the decision they will make.

- Patient enrolment and selection bias.

It might increase patient enrolment and reduce selection bias resulting in better generalizable study results. Meanwhile, should many patients and proxies object against enrolment, this could likewise contribute to selection bias.

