**Specific objectives**

1. To estimate the proportions of patients and proxies that give consent for and object against enrolment in acute stroke trials using deferred consent procedures;
2. To map the workflow and timeline of the deferred consent procedure;
3. To explore the personal feeling of capability of patients and proxies to provide consent for participation in an acute stroke controlled trial;
4. To explore appreciation of patients and proxies of the deferred informed consent procedure;
5. To investigate recall and comprehension by patients and proxies of study methods of the acute stroke trial for which they provided deferred consent;
6. To compare the observations on 1-5 with data from previous acute stroke trials.

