**Handling of data and documents**

The results of this substudy will be reported during the active enrolment in the CONTRAST trials. The conclusions of this substudy may have consequences for the actual consent study procedures.

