**Questionnaire 2 – proxy**

[voor start vragenlijst: informatie deferred consent en redenen voor dit onderzoek]

Enquêtevragen als proxy (familielid of partner) om uitgestelde toestemming is gevraagd voor deelname aan de CONTRAST trial en geen toestemming heeft gegeven.

Wat was de reden dat u geen toestemming heeft gegeven? (niet verplicht)

- Dit wil ik niet zeggen
  
  - Ik wil niet dat er gegevens verzameld worden van mijn partner/familielid
  
  - Ik vond het te veel informatie
  
  - Ik begreep de uitleg niet goed
  
  - Ik voelde mij gestresst
  
  - Deze vraag komt te snel na de beroerte
  
  - Ik heb te weinig bedenktijd gehad
  
  - Ik vind dat iemand anders, namelijk de behandeld arts deze beslissing moet maken
  
  - Ik vind dat iemand anders, namelijk een ander familielid deze beslissing moet maken
  
  - Anders, namelijk: .....
- 
- Geslacht
    - Man
    - Vrouw
  
  - Leeftijd (vrije tekst)
  
  - Wat is uw hoogst genoten opleiding? (keuze)
    - geen
    - basisschool
    - lager beroepsonderwijs (LBO, VMBO)
    - middelbaar algemeen voorbereidend onderwijs (MAVO)

- middelbaar beroepsonderwijs (MBO)
- hoger algemeen voorbereidend, wetenschappelijk onderwijs (HAVO, VWO)
- hoger beroepsonderwijs (HBO)
- kandidaats/propedeuse wetenschappelijk onderwijs (WO)
- (post) wetenschappelijk onderwijs
- weet niet / wil ik niet zeggen

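### Deferred-consent substudy: appreciation of the procedure is measured only in people who consented, and the refusers' form has no rating and no tick option for having been asked only after treatment

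*Protocol*

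**What the plan says.** All of this is in Protocol, Appendix 12 (deferred consent in acute stroke trials).

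- **Objective.** Under Specific objectives, item 4 reads "To explore appreciation of patients and proxies of the deferred informed consent procedure". It is not limited to those who said yes.
- **Foreseen objection.** The section on benefits and drawbacks says that "some patients and proxies will feel capable of making a decision and could object to the deferred consent procedure itself", and adds that this may affect what they decide.
- **Consenters.** The recruitment text (under Duration of data collection) and items 3 to 5 of Study procedures assign felt capability, appreciation and recall to Questionnaire 1. It is sent at three months to the person who gave consent. It contains the rating item "Hoe ervaart u de uitgestelde toestemmingsprocedure? (onderstaande Likert schaal + vrije tekst" (question 21 for patients; the proxy form has the same item as question 20). Question 17 lets respondents say that they would have preferred to be asked before any study procedure, treatment included.
- **Refusers.** "They will be asked to only fill out Questionnaire 2, which concerns the reasons for not giving consent". The same paragraph makes answering voluntary and excludes any further questionnaire or interview.
- **Content of Questionnaire 2.** It has one reasons question and some background items. The only option on when the question was put is "Deze vraag komt te snel na de beroerte". The patient form states that several answers are possible. The proxy form has "Wat was de reden dat u geen toestemming heeft gegeven? (niet verplicht" (not mandatory) and is silent on multiple answers.
- **Use.** The substudy is to be reported while the trials are still enrolling, and "The conclusions of this substudy may have consequences for the actual consent study procedures".

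**The concern.** The people most likely to dislike being enrolled first and asked later are those who then refuse. They are the group from whom no rating is collected. Appreciation is therefore observed in a sample selected on a decision that, by the appendix's own account, dislike of the procedure may influence.

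The reasons list does not close the gap. A refuser who felt able to decide and wanted to be asked before the patch went on has no box to tick. That person has to write it in unprompted, whereas someone who felt asked too early has a ready option. Open text and tick boxes do not collect reasons at the same rate, so the two timing complaints would not be counted on equal terms.

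At stake is how far the substudy's conclusion on appreciation reaches. Recruiting more consenters does not help, because the missing part is not sampling error.

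**Working it through.** The plan gives no figure to reproduce. The check has two parts: an item-by-item comparison of the forms, and an illustration of size that rests on assumed rates.

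**1. The forms side by side**

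| Content | Questionnaire 1 (consenters, 3 months) | Questionnaire 2 (refusers, during admission) |
|---|---|---|
| Likert rating of the deferred procedure | Yes (patient question 21, proxy question 20) | No |
| Should have been asked before all study procedures, including treatment | Yes, closed option (question 17) | No closed option |
| Asked too soon after the stroke | Yes (question 14) | Yes |
| Too little time to think | Yes (question 14) | Yes |
| Free text | Yes | Yes (other, namely) |

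Questionnaire 2 has nine closed reasons: prefer not to say; no data collection wanted; too much information; explanation not understood; stressed; too soon; too little time to think; the physician should decide; a partner or relative should decide. Five of these repeat question 14 of Questionnaire 1, and the two on someone else deciding correspond to question 13. In Questionnaire 1, questions 13 and 14 follow for people who answered at question 12 that they did not feel able to decide. Seven of the nine reasons therefore describe inability to decide. Too little time to think is related to time, but it concerns the length of deliberation and not whether consent came before or after treatment. None of the nine fits a person who felt able to decide and objected to the deferral. The proxy form carries the same list.

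**2. Size, on assumptions only**

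Let *r* be the share who refuse and *a* the share of consenters who approve. Nothing is known about approval among refusers, so approval among all who were asked lies between *a*(1 − *r*) (no refuser approves) and *a*(1 − *r*) + *r* (every refuser approves). The width of that range is *r*.

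- From the protocol: the aim of 300 patients.
- Assumed: *a* = 80%; *r* = 5%, 10% or 20%; the Likert scale cut into approve or not; every consenter answers.
- Sampling interval: full 95% width = 2 × 1.96 × √(0.8 × 0.2 / *n*), with *n* = 300(1 − *r*).

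| *r* | *n* | Lower bound | Upper bound | Unmeasured width | 95% interval width |
|---|---|---|---|---|---|
| 5% | 285 | 0.80 × 0.95 = 76% | 76% + 5% = 81% | 5 points | 9.3 points |
| 10% | 270 | 0.80 × 0.90 = 72% | 72% + 10% = 82% | 10 points | 9.5 points |
| 20% | 240 | 0.80 × 0.80 = 64% | 64% + 20% = 84% | 20 points | 10.1 points |

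Under these assumptions the unmeasured part is smaller than sampling error at 5% refusal, about equal to it at 10%, and about twice as large at 20%.

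**The case against.** Several points on the other side are sound.

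- **The objection can be recorded.** Both versions of Questionnaire 2 end with a free-text option and open with information about deferred consent, so the topic is in view. Protocol section 11.2 also has the reason for refusal, if available, noted in the clinical chart. A reader might infer that the form can never show a wish to be asked before treatment. The documents do not support that. What is missing is a closed item.
- **The substudy is not tilted one way.** A reader might infer that the forms settle in advance which way the consent procedure would change. Question 17 of Questionnaire 1 offers two earlier options against one later option, and the sentence on consequences refers to the whole substudy. Asking before treatment can emerge, although on a closed item only from consenters.
- **Felt capability is partly covered.** Refusers' reasons largely repeat the follow-up questions for people who felt unable to decide. The gap is therefore clearest for objective 4.
- **The drawback is not named as a study question.** The appendix says that people "could object to the deferred consent procedure itself because they not understand the reasons for the postponement of asking consent". It ties the objection to misunderstanding, which the not-understood option touches, and no specific objective names it. That option still records the cause and not the objection.
- **The restriction is deliberate.** Limiting Questionnaire 1 to consenters and keeping the refusers' form short is explicit and sparing of people who have said no. This is a design choice, not a contradiction. It justifies a short form, but not an objective wider than its measurement.
- **Readers can bound the gap.** Objective 1 reports the refusal proportion, and if refusal is low the gap is small.

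**Conclusion.** The point holds in a limited form. Objective 4 is worded for patients and proxies generally but is measured only in those who consented. The refusers' form has no rating and no closed option for having been asked only after treatment, although the appendix foresees that objection and already has the item in question 17.

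The size cannot be derived from the protocol. The illustration rests wholly on assumed refusal and approval rates; on those, the unmeasured range runs from 5 to 20 points. It shows when the gap would matter and does not estimate a bias.

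The consequence is confined to a descriptive, observational substudy under a tertiary objective. The primary outcome, the safety data and the treatment comparison are untouched. It is worth correcting because the change is cheap and because the substudy may alter the consent procedure during enrolment.

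**What to change.** In both versions of Questionnaire 2:

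1. Add one optional tick option that reuses the question 17 wording on being asked before all study procedures, including treatment.
2. Add the existing Likert item on the deferred procedure, marked optional.
3. On the proxy form, state that several answers are allowed, as the patient form already does.

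Report refusers' ratings next to consenters' ratings and do not pool them. Questionnaire 2 is completed during admission and Questionnaire 1 at three months, so a combined figure would mix an immediate rating with a recalled one.

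If the Likert item is not added, reword objective 4 and its conclusions so that they apply to those who consented.

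The cost is about one more minute on a voluntary form that the protocol puts at 5 minutes, and some refusers will leave the items blank. Rewording the objective adds no burden for participants.
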